11.1.2. Serious Adverse Events

A serious adverse event (SAE) based on International Conference on Harmonisation (ICH) and EU Guidelines on Pharmacovigilance for Medicinal Products for Human Use is any untoward medical occurrence that at any dose:

- Results in death (ie, the AE actually causes or leads to death).
- Is life-threatening. Life-threatening is defined as an AE in which the subject was at risk of death at the time of the event. It does not refer to an event which hypothetically might have caused death if it were more severe. If either the investigator or the Sponsor believes that an AE meets the definition of life-threatening, it will be considered life-threatening.
- Requires unplanned in-patient hospitalization >24 hours or prolongation of existing hospitalization.
- Results in persistent or significant disability/incapacity (ie, the AE results in substantial disruption of the subject's ability to conduct normal life functions).
- Is a congenital anomaly/birth defect.
- Is an important medical event that may not result in death, be immediately life-threatening or require hospitalization, but may be considered an SAE when, based upon appropriate medical judgment, the event may jeopardize the subject or subject may require intervention to prevent one of the other outcomes listed in this definition. Examples of such events are intensive treatment in an emergency department or at home for allergic bronchospasm, blood dyscrasias, or convulsion that does not result in hospitalization; or development of drug dependency or drug abuse.

Given that the investigator's perspective may be informed by having actually observed the event, and the Sponsor is likely to have broader knowledge of the drug and its effects to inform its

evaluation of the significance of the event, if either the Sponsor or the investigator believes that the event is serious, the event will be considered serious.

11.1.3. Severity Criteria (Grade 1-5)

Definitions found in the Hematologic Adverse Event Grading Scheme ([Hallek 2008](#)) will be used for grading the severity of hematologic AEs. Refer to [Appendix L](#) for the grading of hematologic AEs.

Definitions found in the Common Terminology Criteria for Adverse Events version 4.03 (CTCAE v4.03) will be used for grading the severity (intensity) of nonhematologic AEs. The CTCAE v4.03 displays Grades 1 through 5 with unique clinical descriptions of severity for each referenced AE. Should a subject experience any AE not listed in the CTCAE v4.03, the following grading system should be used to assess severity:

- Grade 1 (Mild AE) – experiences which are usually transient, requiring no special treatment, and not interfering with the subject’s daily activities
- Grade 2 (Moderate AE) – experiences which introduce some level of inconvenience or concern to the subject, and which may interfere with daily activities, but are usually ameliorated by simple therapeutic measures
- Grade 3 (Severe AE) – experiences which are unacceptable or intolerable, significantly interrupt the subject’s usual daily activity, and require systemic drug therapy or other treatment
- Grade 4 (Life-threatening or disabling AE) – experiences which cause the subject to be in imminent danger of death
- Grade 5 (Death related to AE) – experiences which result in subject death

11.1.4. Causality (Attribution)

The investigator is to assess the causal relation (ie, whether there is a reasonable possibility that the study drug caused the event) using the following definitions:

Not Related: Another cause of the AE is more plausible; a temporal sequence cannot be established with the onset of the AE and administration of the investigational product; or, a causal relationship is considered biologically implausible.

Unlikely: The current knowledge or information about the AE indicates that a relationship to the investigational product is unlikely.

- Possibly Related:** There is a clinically plausible time sequence between onset of the AE and administration of the investigational product, but the AE could also be attributed to concurrent or underlying disease, or the use of other drugs or procedures. Possibly related should be used when the investigational product is one of several biologically plausible AE causes.
- Related:** The AE is clearly related to use of the investigational product.

11.2. Unexpected Adverse Events

An “unexpected” AE is an AE that is not listed in the IB/package insert or is not listed at the specificity or severity that has been observed. For example, hepatic necrosis would be “unexpected” (by virtue of greater severity) if the IB referred only to elevated hepatic enzymes or hepatitis. Similarly, cerebral thromboembolism and cerebral vasculitis would be “unexpected” (by virtue of greater specificity) if the IB/package insert listed only cerebral vascular accidents. “Unexpected” also refers to AEs that are mentioned in the IB as occurring with a class of drugs or as anticipated from the pharmacological properties of the drug, but are not specifically mentioned as occurring with the study drug under investigation.

11.3. Special Reporting Situations

Special reporting situation on a Sponsor study may require expedited reporting and/or safety evaluation include, but are not limited to:

- Overdose of any study drug
- Suspected abuse/misuse of a study drug
- Inadvertent or accidental exposure to a study drug
- Medication error involving a product (with or without subject exposure to the study drug, eg, name confusion)

Occurrence of any special reporting situations should be recorded in the eCRF. If any special reporting situation meets the criteria of an AE, it should be recorded on the AEs eCRF. If the AE is considered serious, it should be recorded on the AEs eCRF as serious and should be reported on the Serious Adverse Event Report Form. The Serious Adverse Event Report Form should be sent via email or fax to Pharmacyclics Drug Safety or designee within 24 hours of awareness.

11.4. Documenting and Reporting of Adverse Events and Serious Adverse Events by Investigators

11.4.1. Assessment of Adverse Events

Investigators will assess the occurrence of AEs and SAEs at all subject evaluation timepoints during the study. All AEs and SAEs whether volunteered by the subject, discovered by study

personnel during subject office visits, detected through physical examination, clinically significant laboratory test, or other means, will be recorded in the subject's medical record and on the AEs eCRF and, when applicable, on the Serious Adverse Event Report Form.

Each recorded AE or SAE will be described by its duration (ie, start and end dates), severity, regulatory seriousness criteria (if applicable), suspected relationship to the investigational product, and any actions taken.

11.4.2. Adverse Event Reporting Period

All AEs whether serious or non-serious, will be documented in the source documents from the time signed and dated ICF is obtained until 30 days following the last dose of study drug. Adverse events noted during Screening period will be recorded in Medical History CRF. SAEs will be reported to the Sponsor on the SAE Report Form from the time of ICF signing until 30 days following the last dose of study drug. Both serious and non-serious AEs will be recorded in the eCRF from the first dose of study drug until 30 days after the last dose of study drug. In the case of subjects who are transferring their ibrutinib treatment from this protocol to another ibrutinib treatment protocol, AE collection under this protocol will stop at the time AE collection starts under the next protocol.

Serious adverse events reported after 30 days following the last dose of study drug should also be reported if considered related to study drug. Resolution information after 30 days should be provided. In the case of subjects who are transferring their ibrutinib treatment from this protocol to another ibrutinib treatment protocol, SAE collection under this protocol will stop at the time SAE collection starts under the next protocol.

Adverse event and SAE collection will also stop at the time any subject starts a subsequent anticancer treatment within the first 30 days after discontinuing ibrutinib.

Progressive disease should NOT be reported as an event term, but instead symptoms/clinical signs of disease progression may be reported. (See [Section 11.1.1](#))

All AEs, regardless of seriousness, severity, or presumed relationship to study drug, must be recorded using medical terminology in the source document. All records will need to capture the details of the duration and the severity of each episode, the action taken with respect to the study drug, investigator's evaluation of its relationship to the study drug, and the event outcome. Whenever possible, diagnoses should be given when signs and symptoms are due to a common etiology (eg, cough, runny nose, sneezing, sore throat, and head congestion should be reported as "upper respiratory infection"). Investigators must assess the relationship of the AE/SAE to the study therapy and record their opinion in the CRF. All measures required for AE/SAE management must be recorded in the source document and reported according to Sponsor instructions.

All deaths should be reported with the primary cause of death as the AE term, as death is typically the outcome of the event, not the event itself. Autopsy and postmortem reports must be forwarded to the Sponsor, or designee, as outlined above, if allowed per local regulatory guidelines.

If a death occurs within 30 days after the last dose of study drug, the death must be reported to the Sponsor as a SAE.

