5.5. Criteria for Permanent Discontinuation of Study Drug

Investigators are encouraged to keep a subject who is experiencing clinical benefit in the study unless significant toxicity puts the subject at risk or routine noncompliance puts the study outcomes at risk. If a subject discontinues one study drug for reasons other than disease progression, the other study drug should be continued per protocol. Refer to Study Design details in [Section 3.1.1](#) and [Section 3.1.2](#). For a complete list of criteria for permanent discontinuation of study treatment, refer to [Section 9.2](#).

An End-of-Treatment Visit ([Section 8.7](#)) is required for all subjects except for those subjects who have withdrawn full consent.

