10.4.11. Safety Analysis

In the MRD cohort, analysis of safety data will be conducted on the all treated population in pre-randomization phase and safety population in the randomization phase. An overall summary across both pre-randomization and randomization phase may also be provided as appropriate. The baseline value is defined as the last value collected on or prior to the first dose date of study drug. In the Fixed Duration cohort, safety analysis will be based on all treated population.

The safety variables to be analyzed include exposure of study drugs, AEs, clinical laboratory test results (hematology and chemistry), ECOG performance, physical examination, and vital signs measurements. In general, continuous variables will be summarized using descriptive statistics (n, mean, median, standard deviation, standard error and range). Categorical variables will be summarized using frequencies and percentages. No formal statistical testing is planned.

Adverse Events

Adverse event parameters to be evaluated are the type, incidence, and intensity of AEs; the relationship of AEs to study treatment; and the action taken with respect to study treatment due to AEs.

The verbatim terms used in the eCRF by investigators to identify AEs will be coded using the Medical Dictionary for Regulatory Activities (MedDRA).

Treatment-emergent period is defined as the period of time from the first dose of study treatment, until the earlier of:

- Thirty days following the last dose of ibrutinib or 30 days following the last dose of venetoclax, whichever occurs later

AND

- The start date of a new anti-cancer therapy.

The treatment-emergent AEs (TEAEs) are those events that:

- Are not present prior to the treatment-emergent period and occur during the treatment-emergent period,
- The onset dates are missing, and end dates are during the treatment-emergent period,
- Are considered related to study drug by the investigator regardless of the start dates of the events, or
- Are present prior to the treatment-emergent period but worsen in severity during the treatment-emergent period or are subsequently considered related to study drug by the investigator.

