11.1. Definitions

11.1.1. Adverse Events

An AE is any untoward medical occurrence in a subject administered a pharmaceutical product and which does not necessarily have a causal relationship with this treatment. An AE can therefore be any unfavorable and unintended sign (including a clinically significant abnormal laboratory finding, for example), symptom, or disease temporally associated with the use of an investigational study drug, whether or not considered related to the study drug ([ICH-E2A, 1995](#)).

For the purposes of this clinical study, AEs include events which are either new or represent detectable exacerbations of pre-existing conditions.

The term "disease progression" should not be reported as an AE term. As an example, "worsening of CLL/SLL" or the clinical diagnosis that is associated with disease progression should be reported.

Adverse events may include, but are not limited to:

- Subjective or objective symptoms provided by the subject and/or observed by the investigator or study staff including laboratory abnormalities of clinical significance.
- Any AEs experienced by the subject through the completion of final study procedures.
- AEs not previously observed in the subject that emerge during the protocol-specified AE reporting period, including signs or symptoms associated with the underlying disease that were not present before the AE reporting period
- Complications that occur as a result of protocol-mandated interventions (eg, invasive procedures such as biopsies).

The following are NOT considered AEs:

- **Pre-Existing Condition:** A pre-existing condition (documented on the medical history CRF) is not considered an AE unless the severity, frequency, or character of the event worsens during the study period.

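### Protocol 11.4.2 stops AE and SAE collection at an early switch to new anticancer therapy, with no exception for 30-day deaths or drug-related SAEs that other rules require or count

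*Protocol*

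**What the plan says.** Protocol 11.4.2 sets the ordinary window: AEs and SAEs are reported until 30 days after the last dose of study drug. Section 7.1.1.5 and the adverse-event footnotes to Appendices A and B give the same 30-day end without mentioning an earlier stop. Section 11.4.2 then adds that AE and "SAE collection will also stop at the time any subject starts a subsequent anticancer treatment within the first 30 days after discontinuing ibrutinib".

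Two other sentences in 11.4.2 point the other way. On deaths: "If a death occurs within 30 days after the last dose of study drug, the death must be reported to the Sponsor as a SAE". On late events: "Serious adverse events reported after 30 days following the last dose of study drug should also be reported if considered related to study drug". Neither excludes subjects on new therapy.

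On the analysis side, Protocol 10.4.11 and SAP Section 5 both end the treatment-emergent period no later than the start of new anticancer therapy. Both also count related events as TEAEs without a date limit. One limb of the protocol definition reads: "Are considered related to study drug by the investigator regardless of the start dates of the events". By default the SAP puts only TEAEs into the AE summaries, and its Table 3 lists SAEs and TEAEs leading to death.

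On progression, Section 11.4.2 says: "Progressive disease should NOT be reported as an event term, but instead symptoms/clinical signs of disease progression may be reported". It refers to Section 11.1.1, which also bars the term and says that worsening of CLL/SLL "or the clinical diagnosis that is associated with disease progression should be reported". For deaths, 11.4.2 adds: "All deaths should be reported with the primary cause of death as the AE term".

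**The concern.** An unconditional stop and an unconditional duty to report apply to the same subject in the same 30 days. Whether a death soon after a switch reaches the sponsor as an SAE then depends on which sentence the site follows. For drug-related events the mismatch reaches the analysis, because the TEAE definitions expect events that the collection rule tells sites not to record.

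Deaths within 30 days and related SAEs are core safety data, and a table of fatal events can be sensitive to single cases. The stop sentence also names only ibrutinib, in a trial where subjects may be on placebo or on venetoclax alone.

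**Working it through.** No figure in the plan bears on this point, so the check is to follow each type of event through the rules. For illustration, take a subject whose last dose of ibrutinib and of all study drug is day 0 and who starts new anticancer therapy on day 10. Each event below begins after the switch.

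| Event | Stop sentence | Other reporting rule in 11.4.2 | TEAE under Protocol 10.4.11 and SAP 5? | What depends on the reading |
|---|---|---|---|---|
| Unrelated death, day 20 | Not collected | Must be reported as an SAE | No: after the period ends | Safety database, listings, narratives |
| Related death, day 20 | Not collected | Must be reported as an SAE | Yes, by relatedness | As above, plus the SAE and fatal-TEAE tables |
| Related non-fatal SAE, day 20 | Not collected | Inside the ordinary window; the late-SAE sentence covers only events after day 30 | Yes, by relatedness | SAE table |
| Unrelated non-fatal SAE, day 20 | Not collected | Inside the ordinary window | No | Nothing in the default TEAE tables |
| Related SAE, day 40 | Unclear | Late-SAE sentence asks for it | Yes, by relatedness | SAE table |

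The first two rows are a direct contradiction. Rows two and three are events the analysis counts and the stop discards. The last row is unreconciled.

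A subject who switches on day 31 instead is never reached by the stop. A related SAE on day 40 in that subject is plainly reportable and is a TEAE. The same kind of event is thus treated differently according to whether the switch fell before or after day 30.

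**The clocks.**

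- The stop sentence runs from discontinuing ibrutinib.
- The reporting window and the death rule run from the last dose of study drug.
- The protocol's treatment-emergent period runs from the later of the last ibrutinib and last venetoclax doses.

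These can differ. Section 5.5 says: "If a subject discontinues one study drug for reasons other than disease progression, the other study drug should be continued per protocol". Section 3.1.1 likewise keeps a subject who has stopped ibrutinib on whatever treatment is tolerated. A subject who stops ibrutinib, stays on venetoclax and switches more than 30 days after ibrutinib does not trigger the stop.

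Under Section 3.1.2, placebo subjects discontinue ibrutinib at randomisation. Read literally, the stop would rarely reach them when they later leave placebo, but it would reach the ibrutinib arm. A site that has not been unblinded cannot tell which applies.

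**The case against.** The strongest reply is that the death rule and the late-SAE sentence are specific duties that override a general stop, so a careful site would report these events anyway. That is a reasonable reading, and the documents do not show that any event has been lost. But the text does not say so, and the late-SAE sentence does not reach a related SAE inside the first 30 days.

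Several limits on the consequences also stand:

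- Unrelated events beginning after new therapy are outside the treatment-emergent period, so the default TEAE tables exclude them whichever sentence is followed.
- Deaths are still captured for survival. Section 8.9 has contact about every 3 months after progression, and OS counts death from any cause.
- No formal safety testing is planned.
- In the MRD cohort, Section 3.1.2 reserves non-study therapy for documented confirmed progression, and both cohorts offer reintroduction of study drug. This should limit early switching.
- The ibrutinib clock does not itself lose events for a subject continuing venetoclax. Where the stop is not triggered, more is collected, not less. It is an inconsistency, not a demonstrated gap.

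A reader might infer that the progression rules cannot all be obeyed for a death from CLL. The documents do not support this. Both sections bar progression as the term, 11.4.2 refers to 11.1.1 for the substitute, and a death reported as worsening of CLL/SLL satisfies all three sentences. What remains is that one section says such events may be reported and the other says they should be.

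A reader might also size the problem from the 5.9% serious-event rate for malignant neoplasm progression in Protocol 1.3.2.2. That comes from venetoclax monotherapy studies that included subjects with 17p deletion and with prior B-cell receptor inhibitor failure. It is not a forecast for treatment-naive subjects on the combination, and it does not measure the effect of a reporting rule.

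**Conclusion.** The contradiction between the stop sentence and the 30-day death rule holds on the plain wording, as does the mismatch with the TEAE definitions for related events. Its reach is limited to related SAEs and related deaths in the TEAE tables, and to the safety database, listings and narratives for 30-day deaths. The primary endpoints of both cohorts, PFS and OS are unaffected.

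The number of events cannot be computed. It would need the share of subjects who switch within 30 days and their rate of death or related SAE in the remaining window, and the documents give neither. The conclusion rests on reading the stop as written. Site instructions that already exempt these events would reduce it to a drafting fault, but none appear in the protocol or SAP. It should be corrected because the data concerned are basic safety data and the correction is easy.

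**What to change.** Replace the stop sentence in Protocol 11.4.2 with text to this effect:

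> After the start of subsequent anticancer therapy, collection of unrelated AEs and SAEs stops, except that deaths within 30 days after the last dose of any study drug (ibrutinib, venetoclax or placebo) and SAEs considered related to study drug are reported regardless of subsequent therapy.

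This removes the conflict with the death rule, makes collection of related SAEs match the TEAE definitions in Protocol 10.4.11 and SAP Section 5, and replaces the ibrutinib clock.

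As a minor clarification, bring the permissive wording on progression-related signs and symptoms in 11.4.2 into line with the firmer wording in 11.1.1, so that serious or fatal events due to progression are recorded under one term. SAP Table 3 needs no change, and deaths from CLL should stay on the AE/SAE record as 11.4.2 requires.

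The cost is a few sentences in the protocol and a note to sites, with no new visits or assessments.

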11.4.3. Expediting Reporting Requirements for Serious Adverse Events

All SAEs (initial and follow-up information) will be reported on the Serious Adverse Event Report Form and sent via email or fax to Pharmacyclics Drug Safety, or designee, within 24 hours of the discovery of the event or information. Pharmacyclics may request follow-up and other additional information from the investigator (eg, hospital admission/discharge notes and laboratory results). The contact information (phone, email, and fax) for Pharmacyclics Drug Safety can be found on the Serious Adverse Event Report Form and instructions.

All SAEs that have not resolved by the end of the study, or that have not resolved upon discontinuation of the subject's participation in the study, must be followed until any of the following occurs:

- The event resolves
- The event stabilizes
- The event returns to baseline, if a baseline value/status is available
- The event can be attributed to agents other than the study drug or to factors unrelated to study conduct.
- It becomes unlikely that any additional information can be obtained (subject or health care practitioner refusal to provide additional information, lost to follow up after demonstration of due diligence with follow-up efforts)

The Sponsor assumes responsibility for appropriate reporting of AEs/SAEs to the regulatory authorities and governing bodies according to the local regulations.

The investigator (or Sponsor where required) must report these events to the appropriate Independent Ethics Committee/Institutional Review Board (IEC/IRB) that approved the protocol unless otherwise required and documented by the IEC/IRB.

